## PROTOCOL REVISIONS AND AMENDMENTS

Protocol Version	Date	Change Initiated by (initials)	Brief description of protocol modifications/ actions requested, if any
Template	9/5/17	TNK, AK	Input from IRB, OCT, MARCH, IND/IDE services, PIs
Draft 1	4/10/17	AK, NS	First draft of the protocol from the template
Draft 2	4/13/17	TNK	Comments up to consent portion of the protocol
Draft 3	6/17/17	AK	Addressing TNK comments, formatting
Draft 4	6/25/17	AK	Responding to IRB comments
Draft 5	8/3/17	TO, AES, AR (ICTR)	ICTR DMC and SMS comments, formatting
Draft 6	8/7/2017	AK	Addressing DMC and SMS comments
Draft 7	8/25/2017	AK	Finalizing protocol
Draft 8	9/12/17	AK	Minor updates
Draft 9	3/23/18	AK	Updates to FMT product
Draft 10	5/22/18	AK	Minor editorial updates
Draft 11	7/31/2018	AK	Responses to FDA comments

Draft 12	9/14/18	AK	Changes requested by IRB
Draft 13	11/26/18	SZ	Changes requested by IRB
Draft 14	12/5/18	AK, IG	
Updates to protocol
 
 
– Inserted protocol number and clinicaltrials.gov number
 
– Corrected typos
 
– Clarified stool collection during intervention period regardless of hospitalization, for all groups
 
– Updated contact information as needed
 
– Clarified CRU nurse is considered a study nurse for the purpose of this study
 
– Clarified fasting allows for clear liquids (not strict NPO)
 
– Updated inclusion for new antibiotic to be started within 72 hours rather than three doses
 
– Clarified 30-minute post-dose observation need only be done for first dose
 
– Study test capsule and pregnancy test (when applicable) will be taken at intervention visit
 
– Defined timeline for exclusion of bowel obstruction or gut motility issues
 
– Clarified exclusion for neutropenia and how/when to evaluate
 
– Further explained recruitment
 
– Change from 19 days to 14 days for cutoff of antibiotic regimen concurrence
 
– Explained withdrawal and early termination visit
 
– Explained accountability recording (med diary) and potential drug return
 
– Clarified concomitant medications, including certain long-term antibiotics
 
– Removed Charlson's Comorbidity Index
 
– Added option to collect perirectal swabs at baseline if needed
 
– Removed phrase "safety assessment" - defined as AE evaluation, which is already listed
 
– Clarified calls during treatment period will be once per week
 

CONFIDENTIAL

## STATEMENT OF COMPLIANCE

The study will be carried out in accordance with Good Clinical Practices (GCP) as required by the following:

- United States Code of Federal Regulations (CFR) applicable to clinical studies (45 CFR Part 46; 21 CFR Part 50, 21 CFR Part 54, 21 CFR Part 56, and 21 CFR Part 312);
- International Conference on Harmonization (ICH) E6; 62 Federal Register 25691 (1997);

Compliance with these standards provides public assurance that the rights, safety and well-being of study subjects are protected, consistent with the principles that have their origin in the Declaration of Helsinki.

All key personnel (all individuals responsible for the design and conduct of this study) have completed Human Subjects Protection Training.

CONFIDENTIAL

## 1. LIST OF ABBREVIATIONS

ADL	Activities of Daily Living
AE	Adverse event
ANCOVA	Analysis of covariance
CAP	Community acquired pneumonia
CDI	C. difficile Infection
CFR	Code of Federal Regulations
CLIA	Clinical Laboratory Improvement Amendments
CRF	Case Report Form
CRO	Contract Research Organization
CRU	Clinical Research Unit
DCC	Data Coordinating Center
DHHS	Department of Health and Human Services
DMC	Data Monitoring Committee
eCRF	Electronic Case Report Forms
FDA	Food and Drug Administration
FFR	Federal Financial Report
FMT	Fecal Microbiome Transplant
GCP	Good Clinical Practice
GLP	Good Laboratory Practices
GMP	Good Manufacturing Practices
GWAS	Genome-Wide Association Studies
HIPAA	Health Insurance Portability and Accountability Act
IB	Investigator's Brochure
ICH E6	International Conference on Harmonisation Guidance for Industry, Good Clinical Practice: Consolidated Guidance
ICMJE	International Committee of Medical Journal Editors
ICU	Intensive Care Unit
IDE	Investigational Device Exemption
IND	Investigational New Drug Application
IRB	Investigational Review Board
ISO	International Organization for Standardization
MDRO	Multidrug Resistant Organism
MOP	Manual of Procedures
MRSA	Methicillin-resistant Staphylococcus aureus
MSDS	Material Safety Data Sheet
NIH IC	NIH Institute & Center
NSAID	Non-steroidal Anti-inflammatory Drug
OHRP	Office for Human Research Protections
PCR	Polymerase Chain Reaction
PI	Principal Investigator
PRC	Pharmaceutical Research Center
QA	Quality Assurance
QC	Quality Control
SAE	Serious Adverse Event
SAP	Statistical Analysis Plan
SMC	Safety Monitoring Committee
SMS	Study Monitoring Service
TNF	Tumor necrosis factor
UTI	Urinary Tract Infection
UW-ICTR	University of Wisconsin Institute for Clinical and Translational Research

VRE	Vancomycin-resistant Enterococcus
-----	--

## 2. STUDY SUMMARY

Title	A phase II randomized, double-blind placebo-controlled trial to determine if fecal microbiota transplantation is efficacious for hospitalized patients with C. difficile infection history during antibiotic treatment
Short Title and Precis	The GRAFT study
Protocol Number	2017-0789
ClinicalTrials.gov number	NCT03621657
Funding Sponsor	Agency for Healthcare Research and Quality (AHRQ) [name] [contact]
Study Product	OpenBiome fecal microbiota preparation capsule [FMT Capsule DE]
Phase	Phase II study
Methodology	Randomized, double-blind, placebo-controlled trial
Study Duration	1 year
Study Center(s)	Single-center, University of Wisconsin Hospitals and Clinics
Objectives	The primary objective of this study is to compare the gut microbiota and clinical outcomes of oral FMT during antibiotic treatment, immediately following antibiotic treatment, and placebo. The second objective is to assess the safety and feasibility of daily oral Fecal Microbiome Transplant (FMT) as a treatment option.
Number of Subjects	30 (1:1:1 randomization), 10 subjects per group
Diagnosis	Changes in the gut microbiota and C. difficile infection (CDI)
Main Inclusion Criteria	Receiving antibiotics for reasons other than CDI following a recent CDI episode (within last 90 days)
Main Exclusion Criteria	Bowel obstruction or gut motility issues, severely immunocompromised, or admitted to the ICU.
Study Product, Dose, Route, Regimen	FMT will be delivered through oral capsules prepared by OpenBiome. It will be administered in one of two ways depending on the arm of the trial. 1) A low dose of 5 capsules per day during antibiotic treatment and for seven days following conclusion of antibiotics. 2) A single dose of 30 capsules (22.5g) of oral FMT will be given 48-72 hours after antibiotic treatment conclusion.
FDA status of product	Encapsulated fecal microbiota preparation (FMT Capsule DE). Please refer to Finch Therapeutics BBMF # 17194.
	Sourced from human-derived microbes. Please refer to OpenBiome BBMF # 15543, Section F.
	IND: 18262

**Duration of administration** Group 1: 5 capsules of oral FMT per day undergoing antibiotic treatment and for 7 days following conclusion of antibiotic treatment.

Group 2: 30 capsules taken 48-72 hours following conclusion of antibiotic treatment

**Reference therapy** Placebo: 5 capsules of oral placebo per day undergoing antibiotic treatment and for 7 days following conclusion of antibiotic treatment.

**Statistical Methodology** All data will be analyzed using SAS and R. Patient characteristics will be summarized using descriptive statistics. To assess changes in the gut microbiota, ANCOVA and linear mixed models will be used for longitudinal measurements. Safety and adverse events will be summarized using descriptive statistics.

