### 5.2. Hypothesis

Specific aim 1: To demonstrate the effects of fecal microbiota transplantation (FMT) compared to placebo on the composition and function of the gut microbiota of hospitalized patients with recent history of CDI and who are currently receiving antibiotic treatment or just completed antibiotic treatment.

Hypothesis: Daily or at completion oral FMT will maintain the diversity and function of the gut microbiome in patients receiving antibiotic treatment.

Specific aim 2: To evaluate the feasibility and safety of concurrent oral FMT and antibiotic treatment in hospitalized patients at high risk for CDI recurrence in a phase II, randomized, controlled trial.

Hypothesis: Patients will be willing to take oral FMT daily or at the completion of antibiotic treatment and oral FMT will be safe for these patients.

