## 7.2. Study Outcome Measures

### 7.2.1. Primary Study Outcome Measures

The primary outcome of the study is the microbial composition and function of the gut following oral FMT treatment during concurrent antibiotic treatment. Microbial composition of the stool will be assessed using 16s rRNA targeted amplicon sequencing at baseline, every three days ( $\pm 1$  day) during hospitalization and during the intervention, and weekly for one month following completion of the FMT intervention. At the same time points, function of the gut microbiome will be assessed using shotgun metagenomics.

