### *All subjects:*

All subjects will provide stool samples every three days after the baseline visit until their FMT intervention is complete and weekly for one month following conclusion of FMT treatment. Patients will also be asked to complete a patient diary daily from enrollment through the first month of follow-up. If a subject is discharged during the study period, he/she will be asked to complete the patient diary from home as well as provide stool samples to be mailed back to the lab for processing. A member of the study team will also call or email patients on a weekly basis during the intervention and follow-up period to remind to complete the stool sample

as well as record any adverse events. If a patient is discharged, vital signs, general health status, and medications at discharge will be assessed through the medical record.

At the end of the 1 month follow-up (last week of providing the weekly, post-FMT stool samples), patients will receive a call assessing the following:

- Clinical assessment by study nurse or physician, specifically evaluating adverse events related to the intervention.
- Data collection at visit:
  - Interim medical history with focus on infectious diseases
  - Concomitant medication
  - Significant changes in diet
  - Changes in stool consistency (Bristol Stool Scale) and frequency
  - General health status
  - Adverse events (NIH criteria)

A table of all study events is provided in Appendix II, 17.2 (Study Calendar).

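### The synopsis and primary outcome describe Group 1 as FMT during antibiotics, but it is FMT during antibiotics and for 7 days after, and the analysis plan does not separate on-antibiotic stools

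*Combined protocol and SAP*

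**What the plan says.** The objective in section 2 is to "compare the gut microbiota and clinical outcomes of oral FMT during antibiotic treatment, immediately following antibiotic treatment, and placebo". Section 7.2.1 uses similar language: "The primary outcome of the study is the microbial composition and function of the gut following oral FMT treatment during concurrent antibiotic treatment".

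The regimens are set out in the same summary:

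- Group 1: "A low dose of 5 capsules per day during antibiotic treatment and for seven days following conclusion of antibiotics".
- Group 2: "A single dose of 30 capsules (22.5g) of oral FMT will be given 48-72 hours after antibiotic treatment conclusion".
- Group 3: "5 capsules of oral placebo per day undergoing antibiotic treatment and for 7 days following conclusion of antibiotic treatment".

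On sampling, section 11.2 says: "All subjects will provide stool samples every three days after the baseline visit until their FMT intervention is complete and weekly for one month". Section 7.2.1 makes both the 3-day and the weekly stools part of the primary outcome. The schematic in section 3 and the calendar in 17.2 put the weekly phase at 4 weeks.

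On analysis, section 2 names ANCOVA and linear mixed models for longitudinal measurements. Section 12.3 names the inverse Simpson index within individuals and Bray-Curtis dissimilarity between groups. Neither gives a time point or a contrast, and neither distinguishes stools taken on antibiotics from stools taken after them.

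Section 6 is worded differently. It speaks of the daily and single-dose regimens and sets the primary objective as oral FMT against placebo.

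**The concern.** No planned arm receives FMT only while on antibiotics. The arm labelled as during antibiotics has a post-antibiotic week, and the stools that make up the primary outcome run through that week and the following month. If the capsules taken alongside antibiotics did nothing, Group 1 could still differ from placebo because of the capsules taken afterwards. Section 5.4 itself attributes the efficacy of FMT to restored diversity, so this alternative is plausible. A Group 1 versus Group 2 difference likewise mixes timing with total dose and schedule, since both arms receive FMT after antibiotics.

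At stake is what a positive Group 1 result may be called. A longitudinal model over all stools would credit post-antibiotic capsules to FMT during antibiotics.

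**Working it through.** **Capsules.** Inputs are from section 2: 5 capsules a day, 7 days after antibiotics, and 30 capsules (22.5 g) in Group 2.

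- Group 1 after antibiotics: 5 × 7 = 35 capsules. At 22.5/30 = 0.75 g each, 35 × 0.75 = 26.25 g. Ratio to Group 2: 35/30 = 1.17.
- When Group 2 is dosed at 48 to 72 hours, Group 1 has taken 5 × 2 = 10 to 5 × 3 = 15 of these.
- With r antibiotic days remaining at baseline, the post-antibiotic share of Group 1's capsules is 35/(5r + 35) = 7/(r + 7). This is 64% at r = 4, 50% at r = 7, 41% at r = 10 and 33% at r = 14.

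**Stools.** The documents give no distribution of course length, so it is assumed over their range. Section 8.4.1 targets courses of two weeks at most, and section 8.2 allows up to 72 hours of antibiotic before enrolment. Stools are placed on days 3, 6, 9 and so on up to day r + 7, plus 4 weekly stools. A stool on day r or earlier counts as on-antibiotic.

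| Course (days) | Enrolled on antibiotic day | r | On-antibiotic | 7-day tail | Weekly | Share after antibiotics |
|---|---|---|---|---|---|---|
| 3 | 0 | 3 | 1 | 2 | 4 | 6/7 = 86% |
| 3 | 3 | 0 | 0 | 2 | 4 | 6/6 = 100% |
| 5 | 0 | 5 | 1 | 3 | 4 | 7/8 = 88% |
| 5 | 3 | 2 | 0 | 3 | 4 | 7/7 = 100% |
| 7 | 0 | 7 | 2 | 2 | 4 | 6/8 = 75% |
| 7 | 3 | 4 | 1 | 2 | 4 | 6/7 = 86% |
| 10 | 0 | 10 | 3 | 2 | 4 | 6/9 = 67% |
| 10 | 3 | 7 | 2 | 2 | 4 | 6/8 = 75% |
| 14 | 0 | 14 | 4 | 3 | 4 | 7/11 = 64% |
| 14 | 3 | 11 | 3 | 3 | 4 | 7/10 = 70% |

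Over every r from 0 to 14 the minimum is 6/10 = 60%, at r = 12 and 13.

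**Sensitivity to the convention.** Suppose instead that days 0 to r − 1 are concurrent, days r to r + 6 are the tail, and a stool counts as after once a post-antibiotic capsule has been taken. The shares are then 100% at r of 3 or less, 6/7 = 86% at r = 5, 6/8 = 75% at r = 7 and 6/10 = 60% at r = 14. The ±1 day window moves individual stools but not the majority.

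**Alignment of the weekly stools.** They are counted from the end of FMT. In Group 1 they fall 7 + 7 = 14 to 7 + 28 = 35 days after antibiotics. In Group 2 they fall 2 + 7 = 9 to 3 + 28 = 31 days after. Matching week numbers is therefore not matching time since antibiotics.

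**What remains clean.** Stools taken on antibiotics (0 to 4 per patient in these counts) precede every post-antibiotic capsule. On them Group 1 has had FMT, Group 3 has had placebo on the same schedule, and Group 2 is still undosed.

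**The case against.** The label is mostly confined to the synopsis and 7.2.1. Section 6, section 7.1 and the aim 1 hypothesis in 5.2 all speak of daily and one-time or at-completion FMT, which are regimen comparisons and are valid as such. The 7-day tail is stated beside the objective and again in sections 3, 5.5, 7.1 and 11.2. Longitudinal models are named, on-antibiotic stools are collected in all arms, and section 12.1 calls this a pilot not sized for a hypothesis test. All of this stands, and it limits the point to labelling and one unspecified contrast.

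Several stronger readings are tempting, and the documents do not support them:

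- A reader might infer that the trial can say nothing about FMT during antibiotics. The on-antibiotic stools do address it.
- A reader might infer that the plan claims to isolate timing. No section says so, and the arms differ openly in dose and schedule.
- A reader might take 35 against 30 as the defect itself. Any post-antibiotic capsule would create the overlap, and 35 over a week is not like-for-like with 30 at once.
- A reader might extend the point to aim 2, "To evaluate the feasibility and safety of concurrent oral FMT and antibiotic treatment in hospitalized patients". Group 1 patients do take capsules while on antibiotics, so feasibility and tolerance are observed directly.

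The objection does not remove the mismatch in 7.2.1 or the silence of 12.3 on which stools bear on the during-antibiotics question.

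**Conclusion.** The point holds as a mismatch between label and regimen that the analysis plan leaves unresolved. For courses within 14 days, about 60% to 100% of Group 1's scheduled post-baseline stools fall after antibiotics. The figure rests on assumed course lengths, enrolment on antibiotic day 0 to 3, nominal sampling days and full stool return. The majority holds throughout that range under both counting rules. All-stool comparisons can be read as whole regimens against placebo or against each other. They cannot carry a statement about FMT during antibiotics or about timing.

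Courses over 14 days are outside this count. Section 8.4.2.2 stops daily capsules at 14 days of antibiotics, which for those individuals removes the post-antibiotic week. That is an exception for individual patients, not an arm.

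**What to change.** 1. In sections 2 and 7.2.1, name Group 1 as daily FMT during and for 7 days after antibiotics, and describe the all-stool comparisons as comparisons of whole regimens in all randomized patients. Section 6 needs no change on this point.
2. In section 12.3, pre-specify a separate baseline-adjusted contrast of Group 1 with placebo on stools collected before the first post-antibiotic capsule, for example each patient's last on-antibiotic stool. Placebo follows the same capsule schedule, so the cut applies identically in both arms. Rest any statement about FMT during antibiotics on this contrast.
3. Report by arm how many patients have no such stool.
4. Separately, reconcile the group numbers in section 8.4.2.2. For courses over 14 days it assigns the 30-capsule dose to Group 1 and stops daily capsules in Groups 2 and 3. Section 7.1 defines Group 1 as daily FMT and Group 2 as the single dose.

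Cost: objective and analysis wording only, with no change to dosing or sampling. The added contrast uses about 0 to 4 stools per patient in arms of 10 (8 expected to be analyzed, section 12.2), so it is imprecise. Which patients contribute depends on antibiotic duration and stool return, both observed after randomization, so the arms may no longer be balanced. It should therefore be labelled supportive and fixed before any outcome data are seen.

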### 3. SCHEMATIC OF STUDY DESIGN

Baseline/ Day 0  
Recruitment/Consent

Obtain informed consent. Screen potential subjects by inclusion and exclusion criteria; obtain history, document (n=30).

Day 1  
Randomization into trial

Randomize 30 patients

Daily FMT  
dose  
(n=10)

Single  
FMT dose  
(n=10)

Placebo  
(n=10)

Days 2-60  
Intervention

Collect stool samples every 3 days during intervention period and once per week following conclusion of FMT treatment. Detection of incident CDI and *C. difficile* colonization.

For daily FMT: deliver 5 capsules of oral FMT every day for duration of antibiotic treatment + 7 days  
For single dose FMT: deliver oral FMT dose (30 capsules) 48-72 hours post completion of antibiotic treatment.  
For placebo: deliver 5 capsules of placebo capsules every day for duration of antibiotic treatment + 7 days

Intervention End

Occurs when patient completes intervention  
Patient will continue to provide stool samples weekly for 4 weeks

Study End (6 months  
post FMT completion)

Phone call assessing any new medical conditions or adverse events occurring since the last visit.

## 5. BACKGROUND AND INTRODUCTION

This document is a protocol for a human research study. This study is to be conducted according to US and international standards of Good Clinical Practice (FDA Title 21 part 312 and International Conference on Harmonization guidelines), applicable government regulations and Institutional research policies and procedures.

### 5.1. Background and Rationale

Antibiotics have been the leading treatment for bacterial infections over several decades. Unfortunately, antibiotic use in healthcare has led to microbial adaptation, resulting in increasing rates of antibiotic resistant organisms. *Clostridium difficile* is resistant to many antibiotics used to treat infections and therefore proliferates in the intestine of the host during antibiotic treatment. Recent data suggests that *C. difficile* has replaced other antibiotic resistant organisms, such as methicillin-resistant *Staphylococcus aureus*, as the most common etiologic agent for infections in acute care facilities. Of the 2-million people in the U.S. that acquire serious healthcare-acquired infections each year, half a million were due to *C. difficile* infection (CDI), claiming nearly 29,000 lives within 30 days of diagnosis. Additional analyses by the National Hospital Discharge Survey, Annual Files, found that rates of CDI among hospitalized patients aged  $\geq 65$  years increased 200%.

Gut microbiota disruption is fundamental to CDI pathogenesis. The gut microbiota is a symbiotic community of microorganisms that play an integral role in preventing pathogen colonization and infection, a feature termed colonization resistance. The pressures of antibiotic use in healthcare settings lead to alterations in native gut microbiota, resulting in loss of colonization resistance. This is especially relevant for acute care hospitals, where susceptible patients are exposed to heavy antibiotic pressure, diet changes, invasive procedures and *C. difficile*. The mitigation and prevention of CDI is a major challenge. Despite treatment with antibiotics metronidazole and vancomycin, recurrence occurs in 24 to 65% of patients. Approximately 12% of patients will experience an additional recurrence and 6% will experience more than two. Concurrent antibiotic use serves as a trigger for recurrent CDI.

### 5.2. Hypothesis

Specific aim 1: To demonstrate the effects of fecal microbiota transplantation (FMT) compared to placebo on the composition and function of the gut microbiota of hospitalized patients with recent history of CDI and who are currently receiving antibiotic treatment or just completed antibiotic treatment.

Hypothesis: Daily or at completion oral FMT will maintain the diversity and function of the gut microbiome in patients receiving antibiotic treatment.

Specific aim 2: To evaluate the feasibility and safety of concurrent oral FMT and antibiotic treatment in hospitalized patients at high risk for CDI recurrence in a phase II, randomized, controlled trial.

Hypothesis: Patients will be willing to take oral FMT daily or at the completion of antibiotic treatment and oral FMT will be safe for these patients.

